Target lesions. All measurable lesions up to a maximum of 2 lesions per organ and 5 lesions in total, representative of all involved organs, should be identified as target lesions and recorded and measured at baseline. Target lesions should be selected on the basis of their size (lesions with the longest diameter), be representative of all involved organs, but in addition should be those that lend themselves to reproducible repeated measurements. It may be the case that, on occasion, the largest lesion does not lend itself to reproducible measurement in which circumstance the next largest lesion which can be measured reproducibly should be selected. A sum of the diameters (longest for non-nodal lesions, short axis for nodal lesions) for all target lesions will be calculated and reported as the baseline sum diameters. If lymph nodes are to be included in the sum, then only the short axis is added into the sum. The baseline sum diameters will be used as reference to further characterize any objective tumor regression in the measurable dimension of the disease.

Non-target lesions. All other lesions (or sites of disease) including any measurable lesions over and above the 5 target lesions should be identified as non-target lesions and should also be recorded at baseline. Measurements of these lesions are not required, but the presence, absence, or in rare cases unequivocal progression of each should be noted throughout follow-up.

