RECIST 1.1 definitions for assessment of non-target lesions apply. The response of non-target lesions primarily contributes to the overall response assessments of irCR and irNon-CR/Non-PD (irNN). Non-target lesions do not affect irPR and irSD assessments. Only a massive and unequivocal worsening of non-target lesions alone, even without progress in the TMTB is indicative of irPD. In alignment with RECIST 1.1, baseline selected non-target lesions can never convert to measurable lesions, not even if they increase in size at subsequent time points and become measurable. Only true new lesions can be measured and contribute to the TMTB.

C. Follow-up for New Non-Measurable Lesions

All new lesions not selected as new measurable lesions are considered new non-measurable lesions and are followed qualitatively. Only a massive and unequivocal progression of new non-measurable lesions leads to an overall assessment of irPD for the time point. Persisting new non-measurable lesions prevent irCR.

III Overall Assessments for irRECIST

The irRECIST overall tumor assessment is based on TMTB of measured target and new lesions, non-target lesion assessment and new non-measurable lesions.

At baseline, the sum of the longest diameters (SumD) of all target lesions (up to 2 lesions per organ, up to total 5 lesions) is measured. At each subsequent tumor assessment (TA), the SumD of the target lesions and of new, measurable lesions (up to 2 new lesions per organ, total 5 new lesions) are added together to provide the total measurable tumor burden (TMTB).

Overall Assessments by irRECIST	
Complete Response (irCR)	Complete disappearance of all measurable and non-measurable lesions. Lymph nodes must decrease to < 10 mm in short axis.
Partial Response (irPR)	Decrease of $\geq 30\%$ in TMTB relative to baseline, non-target lesions are irNN, and no unequivocal progression of new non-measurable lesions 
 If new measurable lesions appear in subjects with no target lesions at baseline, irPD will be assessed. That irPD time point will be considered a new baseline, and all subsequent time points will be compared to it for response assessment. irPR is possible if the TMTB of new measurable lesions decreases by $\geq 30\%$ compared to the first irPD documentation

Date:

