	
 irRECIST can be used in the adjuvant setting, in subjects with no visible disease on CT/MRI scans. The appearance of new measurable lesion(s) automatically leads to an increase in TMTB by 100% and leads to irPD. These subjects can achieve a response if the TMTB decreases at follow-up, as a sign of delayed response. Based on the above, sponsors may consider enrolling subjects with no measurable disease and/or no visible disease in studies with response related endpoints.
Stable Disease (irSD)	Failure to meet criteria for irCR or irPR in the absence of irPD
Progressive Disease (irPD)	
Minimum 20% increase and minimum 5 mm absolute increase in TMTB compared to nadir, or irPD for non-target or new non-measurable lesions. .
 
 In irRECIST a substantial and unequivocal increase of non-target lesions is indicative of progression. IrPD may be assigned for a subject with multiple new non-measurable lesions if they are considered to be a sign of unequivocal massive worsening
Other	
irNE: used in exceptional cases where insufficient data exist.
 
irND: in adjuvant setting when no disease is detected
 
irNN:, no target disease was identified at baseline, and at follow-up the subject fails to meet criteria for irCR or irPD

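### Two irRECIST rules conflict with the protocol's own text, on non-target lesions in partial response and on the axis used for nodes, so a patient treated beyond progression can be put in the wrong response category

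*Combined protocol and SAP*

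**What the plan says.** The irRECIST response rate in each arm is a secondary endpoint (Section 2.1). Section 14.0 reports it with an exact 90% interval and relies on the irRECIST description to separate responders from non-responders. The assessment is made only for patients who continue treatment beyond progression.

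**Non-target lesions.** Part II.B of the irRECIST text in Section 12.4 introduces irNN as Non-CR/Non-PD and says "Non-target lesions do not affect irPR and irSD assessments". The irPR row of the table that follows asks for a fall of at least 30% in TMTB and also that "non-target lesions are irNN, and no unequivocal progression of new non-measurable lesions". The irCR row requires "Complete disappearance of all measurable and non-measurable lesions". The irSD row is a catch-all: "Failure to meet criteria for irCR or irPR in the absence of irPD".

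**Nodes.** Part III of the same text starts from "the sum of the longest diameters (SumD) of all target lesions" and adds new measurable lesions to obtain TMTB, with no exception for nodes. Part I says that baseline measurement of lesions and nodes follows RECIST 1.1. Section 12.2 gives that rule for the target sum: "longest for non-nodal lesions, short axis for nodal lesions". It adds that nodes are measured and followed by short axis alone, at baseline and afterwards.

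**The concern.** A scoring rule for a listed endpoint should put each set of scans in one category. Here two instructions on the same matter disagree in two places.

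In the first, following the table penalizes the better outcome: complete disappearance of non-target disease costs the patient her partial response, and residual non-target disease does not. In the second, the percentage change that decides irPR depends on which axis the analyst takes for a nodal target, and the resulting burden may not be comparable with the RECIST 1.1 sum in the same patient.

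What is at stake is the reproducibility of one secondary rate per arm.

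**Working it through.** The plan gives no figure on this point, so there is none to reproduce. The first check is logical and the second is arithmetic on assumed lesion sizes.

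**Check 1: non-target disease gone, target disease reduced but still present, no irPD.**

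| Step | Following the sentence in II.B | Following the irPR row |
|---|---|---|
| TMTB down at least 30% | met | met |
| Non-target status is CR | has no bearing on irPR | is not Non-CR/Non-PD, so the condition fails |
| irCR | no, target disease remains | no, target disease remains |
| irPD | no | no |
| Category | irPR (responder) | irSD by the catch-all (non-responder) |

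The same scans give two categories. The error in the irPR row runs in one direction only, towards non-response.

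**Check 2: which axis enters the sum.** Change = (follow-up - baseline) / baseline, with irPR needing -30% or lower. Assume no new measurable lesion contributes. All sizes are illustrative and not from the documents.

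| Example (long x short axis, mm) | Short axis for nodes (Section 12.2) | Longest diameter (Section 12.4, part III) |
|---|---|---|
| A. One target node, 30 x 20 to 25 x 13 | 13/20 - 1 = -35%: irPR | 25/30 - 1 = -17%: irSD |
| B. One target node, 30 x 20 to 20 x 15 | 15/20 - 1 = -25%: irSD | 20/30 - 1 = -33%: irPR |
| C. Node 25 x 20 to 22 x 12, plus a non-nodal lesion 30 to 23 | (12 + 23)/(20 + 30) - 1 = 35/50 - 1 = -30%: irPR | (22 + 23)/(25 + 30) - 1 = 45/55 - 1 = -18%: irSD |

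A and B cross the threshold in opposite directions. C shows that a non-nodal target in the sum does not remove the problem.

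Mixing the axes is worse. A node of 28 x 20 mm that shrinks to 22 x 12 mm, taken by short axis at baseline (20 mm) and by longest diameter at follow-up (22 mm), gives 22/20 - 1 = +10%. By short axis throughout it gives 12/20 - 1 = -40%.

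**Size.** One reclassified patient moves the rate by 1/n. The documents do not say how many patients will be assessed, so n is an assumption:

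- n = 40 (a full arm): 2.5 points
- n = 15: 6.7 points
- n = 10: 10 points
- n = 5: 20 points

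For scale, with n = 15 the exact 90% interval is 0.3% to 27.9% for one responder and 2.4% to 36.3% for two. A one-patient shift is small against that width.

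**The case against.** The best defense is that a sensible reader would reach the right answer. The II.B sentence states the rule directly. The protocol's own RECIST 1.1 table in Section 12.4 uses the same shorthand: its target-PR row also omits non-target CR. For nodes, Section 12.2 has only the short axis followed, so the nodal long axis at follow-up would normally not be recorded, and part III reads as loose wording. The irRECIST text itself uses the short axis for irCR and for selecting new nodes.

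Much of this stands as evidence of intent, and it is why the point is minor. It does not remove the conflict. Under RECIST 1.1 in this protocol, stable disease requires too little shrinkage for PR, so a patient with a 30% fall does not land there by omission. The irSD row, by contrast, catches everyone who misses irPR. And if nodal long axes are not recorded, the sum defined in part III cannot be formed from the planned measurements, which is itself a reason to correct it.

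A reader might also infer that no patient can ever reach irPR. The last row of the table explains irNN as "no target disease was identified at baseline, and at follow-up the subject fails to meet criteria for irCR or irPD", and Section 6.2 requires every patient to have a target lesion. The documents do not support that inference. The last row describes a whole-patient category, whereas the irPR row applies irNN to lesions. The RECIST tables in Section 12.4 likewise use Non-CR/Non-PD both as a lesion status and as an overall response.

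Finally, the irRECIST text is presented as following a cited publication that is not available here, so an edit should be checked against it.

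**Conclusion.** The rules are wrong as written in two places, and the consequence is minor. Read literally, the irPR row scores a patient with at least a 30% TMTB fall, residual target disease and complete non-target disappearance as irSD, against the sentence in II.B. The tumor-burden sum uses longest diameters for all targets, against the short-axis rule for nodes, and can move a patient with nodal targets across the 30% threshold.

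A reader might infer that the errors run mostly towards non-response. That holds for the non-target conflict but is not shown for nodes: examples A and B err in opposite directions, and the documents give no basis for saying which is commoner.

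Nor does the point reach the trial's conclusions. Section 12.4 says that the efficacy objectives are evaluated by unmodified RECIST 1.1. The ORR and PFS decision rules and the choice between arms in Section 14.0 do not use irRECIST. To be affected, a patient must be treated beyond progression and then have either the non-target pattern in Check 1 or nodal targets whose two axes fall on opposite sides of the threshold. How many will is unknown. The lesion sizes and the smaller denominators above are assumptions.

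**What to change.** Make two edits to the irRECIST text in Section 12.4:

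1. In the irPR row, replace the requirement that non-target lesions be irNN with *no irPD of non-target lesions*. Keep the existing condition on new non-measurable lesions. This agrees with II.B and still lets unequivocal non-target worsening override.
2. In part III, define SumD and TMTB, at baseline and at every follow-up, as the sum of diameters ("longest for non-nodal lesions, short axis for nodal lesions"), as Section 12.2 already does.

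Optionally, label the irNN entry in the last row of the table as a whole-patient category, and correct the pointer in Section 14.0, which sends the reader to Section 12.3 for irRECIST.

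Check the wording against the cited irRECIST source and state any deliberate departure from it. The cost is a short text amendment: no new data, and no change to sample size, power or the decision rules. Any irRECIST calls already made should be re-derived from the recorded measurements.

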12.5 Biomarker Assessment

The study will include analyses of archival tumor tissue and peripheral blood to define the biomarkers that could predict/correlate with response. Research bloods will be collected pre-treatment at 4 pre-specified time points: Day 1, Day 8, Day 29, Day 57, with a window of -3 Days for each draw. 6 CPT tubes will be collected at each time point.

12.5.1 Tissue PD-L1 expression (**MedImmune**)

The levels of PD-L1 expression in tumor cells and tumor-infiltrating immune cells will be assessed using SP263 antibody on archival tissue

12.5.2 Tissue gene expression profiling and IHC (**MSKCC, [name], [name] lab**)

By using Nanostring nCounter PanCancer Immune Profiling Panel, and immunofluorescence microscopy, archival tumor tissue will be assessed for tumor infiltration with various immune cell subsets, including CD8 cells, CD4+ effector cells (FoxP3-), CD4+ regulatory T cells (FoxP3+), and myeloid cells (CD68+). Tumors will also be assessed for the expression of the known activating co-stimulatory receptors such as 4-1BB (CD137), OX40, GITR, CD40, and ICOS, as well as known immuneinhibitory components such as PD-L1, indoleamine dioxygenase (IDO), B7-H3, B7-H4, LAG3, TIM-3, PD-1, CTLA-4, VISTA, and BTLA. The expression of each gene will be treated as a continuous variable. For exploratory biomarker analyses, patients will be dichotomized on the basis of the primary efficacy endpoint.

12.5.3 PBMC immunophenotyping (**MSKCC: IMF**)

By using multi-parameter flow cytometry, we will explore whether peripheral blood biomarkers could serve as early predictors of clinical benefit and provide targets for further combinations, with a particular focus on targetable markers of T cell activation (ICOS, CD137, OX40, GITR), and inhibition (LAG3, TIM3, PD-1, BTLA, VISTA), as well as percentages of peripheral inhibitory immune subsets such as MDSCs and Tregs.

Date:

12.5.4 PBMC gene expression analyses (**MSKCC, [name], [name] lab**)

RNA extracted from PBMCs collected at baseline and on-treatment will be analyzed on the Nanostring platform using Nanostring nCounter PanCancer Immune Profiling Panel, to define gene signatures associated with clinical benefit.

12.5.5 PBMC T cell receptor (TCR) repertoire analyses (**MSKCC: IMF, [name], [name] lab**)

Maintenance and expansion of particular T cell receptor (TCR) clones in the peripheral blood may be associated with clinical response. PBMC's collected during the study will be banked for potential future TCR repertoire analyses. DNA isolated from PBMC's will be send for deep sequencing of TCR CDR regions at Adaptive Biotechnologies to determine whether maintenance or emergence of particular oligoclonal populations of T cells in the periphery is predictive of clinical benefit.

12.5.6 Plasma assays

Plasma collected with PBMCs will be stored for additional analyses. Current PBMC-based assays are cumbersome and suffer from variability due to differences in PBMC collection. Plasma-based analyses will include analyses of circulating tumor DNA and RNA, multiplex cytokine ELISAs, and serologic assays for antibodies to specific tumor-associated antigens.

12.5.7 Future research

Leftover blood and tissue samples from the study will in addition be stored for future research using the assays currently in development, including new single-cell based technologies. The future research will continue to be directed towards evaluation of potential novel biomarkers of response/resistance to durvalumab and durvalumab/tremelimumab combination.

13.0 CRITERIA FOR REMOVAL FROM STUDY

Patients may withdraw from the study at any time. Any patient who withdraws will be encouraged to return to the study center for a treatment completion visit. Patients who discontinue early should return within 30 days following the final dose of study treatment. The primary reason for discontinuation must be recorded in the medical record.

Permanent discontinuation of treatment with Durvalumab and Tremelimumab

An individual subject will not receive any further investigational product if any of the following occur in the subject in question:

- Disease progression, per investigator assessment
- Intolerable toxicity of study drugs
- Withdrawal of consent or lost to follow-up
- Adverse event that, in the opinion of the investigator or the sponsor, contraindicates further dosing
- Subject is determined to have met one or more of the exclusion criteria for study participation at study entry and continuing investigational therapy might constitute a safety risk
- Pregnancy or intent to become pregnant
- Grade \geq 3 infusion reaction

Date:

- Initiation of alternative anticancer therapy including another investigational agent

Other reasons for patient discontinuation may include, but are not limited to, the following:

- Change in patient eligibility
- Non-compliance
- Patient decision
- If treatment is delayed for more than 28 consecutive days
- Withdrawal of consent
- If consent is withdrawn, the subject will not receive any further investigational product or further study observation.
- The investigator has the right to discontinue a patient from the study for any medical condition that the investigator determines may jeopardize the patient's safety if he or she continues in the study; for reasons of noncompliance (e.g., missed doses, visits); or if the investigator determines it is in the best interest of the patient.

14.0 BIOSTATISTICS

This Phase 2 study aims to assess the activity of Durvalumab alone and in combination with Tremelimumab in patients with recurrent or persistent endometrial carcinomas or endometrial carcinosarcomas. Patients will be randomized to Arm 1: Durvalumab (anti-PD-L1 Antibody) alone or Arm 2: Durvalumab with Tremelimumab (anti-CTLA-4 antibody). This is a randomized study however it is not powered to show superiority of one arm versus another.

In this study, all analyses will be performed by treatment arm.

To date, there are no published studies of immune checkpoint inhibitors in this patient population.

Extrapolating from prior monotherapy studies of immune checkpoint inhibitors in ovarian cancer have yielded overall response rates in the range of 10-15%, and may serve as a basis for historical comparison of the doublet tested here.

Study	N	ORR (CR+PR)	DCR (ORR+SD)	Prior Therapy
Nivolumab (anti-PD-1) 1 mg/kg q 2 weeks (cohort 1) 3 mg/kg q 2 weeks (cohort 2)	10 10	15% (3/20): 10% (1 PR) 20% (2 CR)	50% (5 SD +1 PR) 40% (2 SD +2 CR)	≥ 2 priors Platinum Resistant
Avelumab (anti-PD-L1) Phase Ib expansion cohort 10 mg/kg q 2 weeks	75	10.7% (8 PR)	55% (33 SD +8 PR)	med 4 priors(1-11) Platinum Resistant
Pembrolizumab (anti-PD-1) Phase Ib expansion cohort 10 mg/kg q 2 weeks	26	11.5% (1 CR, 2 PR)	35% (9 SD+1CR+2 PR)	>80% ≥ 4 priors PD-L1+ (IHC)

ORR (defined as CR+PR) will be the primary endpoint. A 10% ORR will be considered low and 25% or higher will be considered promising for further studies. Forty patients provide 90% power and Type I error of 10% using a Simon two stage minimax design. There will be an interim analysis after evaluable 27 patients and if 3 or more responders (CR+PR) are observed out of evaluable 27 patients then the study will continue to the second stage. At the end of the study we require 7 or more responders out of 40 patients to declare this study positive and the arm worthy for further investigation.

Unacceptable response rate: 0.1

Date:

Desirable response rate: 0.25
Error rates: Type I = 0.1 ; Type II = 0.1

# responses required in Stage I	# patients accrued at stage I	# responses required in Stage 2	Total sample size
≥ 3	27	≥ 7	40

If the test for ORR is significant, then the PFS rate at 24 weeks (+/- 1 week) will also be tested against the historical control estimate. For PFS rate at 24 weeks (+/- 1 week), we consider a 15% rate as low, and a rate of 35% or higher as indicative of promising activity. This stems from Gynecologic Oncology Group studies of the same patient population we are evaluating in this study which have deemed PFS at 6 months of 15% or less as indicative of lack of activity and PFS at 6 months of 35% or more as indicative of having activity.

This test of PFS rate will be performed only if the ORR analysis is significant, and thus PFS assessment is supplementary to ORR assessment. At the end of the study, if 10 or more out of 40 patients are considered progression free at 24 weeks (+/- 1 week), then that arm will be considered worthy of further study. This study will have 94% power and 7% Type I error to show activity in terms of 6 months PFS rate. The overall Type I error of the study is bounded by the 10% error rate of the first hypothesis of ORR. The hierarchy in the two hypotheses for ORR and PFS ensures the overall error rate to be smaller than 10% (Bretz 2009)

If both arms have ≥ 7 responders the winning arm is the one with higher ORR and if both arms have exactly 7 responders the winning arm will be decided based on the review of all efficacy data (ORR and PFS) and the total safety profile (number and type of grade 3 AE) of each arm.

A treatment arm will be considered promising if the ORR decision rule is met, but the 6 month PFS decision rule is not met. After first stage accrual is complete, we will halt the study for 16 weeks after last patient has been accrued to first stage in order to assess the decision rules to move to stage 2. Based on historical accrual rates in similar populations, we anticipate successful enrollment of 4 patients per month yielding a total accrual time of 20 months. Accrual will continue until 40 patients on each arm (evaluable patients are defined in section 12.1), unless the interim analysis after 27 patients does not support continuation.

Definitions of Statistics to be Reported

- Clinical Benefit Rate (CBR), defined as the percentage of patients with complete response (CR) + partial response (PR) + stable disease (SD) by 24 weeks from the start of treatment will be reported and the 90% confidence interval will be estimated using exact binomial proportions. This will be done following RECIST criteria.
- Progression free survival (PFS), defined as the duration of time from start of treatment to time of recurrence, progression, or death due to any cause, whichever occurs first. Patients will be censored at last follow up date. The Kaplan Meier estimate of median PFS will be reported as well as the PFS rate at 24 weeks (+/- 1 week).
- Duration of response (DOR), defined as the time from which measurement criteria are met for CR or PR (whichever status is recorded first using RECIST) until the first date of documented

Date:

disease progression, will be estimated using the Kaplan Meier method. Patients without documented progression will be censored at last follow up.

- The rate of response using immune response criteria (refer to irRECIST description in section 12.3, which defines responders and non responders) and the 90% confidence interval will be estimated using exact binomial proportions.
- Adverse events by the current version of Common Terminology Criteria for Adverse Events version 4 (CTCAE v4.03) will be tabulated in order to assess the safety profile and tolerability therapy in treated patients.

Safety Analysis

The frequency and severity of observed adverse effects will be evaluated. The rates of irAE, SAE, therapy completion rate, and protocol completion will also be reported.

Safety will be measured by the frequency of grade 3 or 4 treatment-related clinically significant toxicities (NCI Common Terminology Criteria for Adverse Events version 3.0), aside from Grade 3 or 4 hematologic or laboratory abnormalities, unless they are deemed unexpected or clinically significant.

Frequencies of toxicities will be tabulated. The grade 3 or 4 treatment-related non-hematologic/non-laboratory toxicity will be estimated at the end of the trial along with the 95% confidence interval. With 40 patients per arm, these rates can be estimated within $\pm 16\%$.

Methods of Efficacy Analysis

Efficacy Variables

The intent of this protocol is to assess checkpoint inhibitors for activity in patients with carcinomas advanced, recurrent endometrial carcinomas and carcinosarcomas.

The principal parameters employed to evaluate the efficacy of the two arms are:

- The rate of ORR and duration of overall objective response (ORR = CR + PR).
- Progression-free survival rate at 24 weeks for all patients evaluable for this endpoint.
- Clinical Benefit Rate (CBR) will be defined as ORR + Stable Disease (SD) rate by 24 weeks.

Patients who have measurable disease present at baseline, have received at least one cycle of therapy, and have had their disease reevaluated will be considered evaluable for response and PFS. The primary efficacy analysis will include only patients who are evaluable for response. Patients without post baseline assessment of response will be included in a sensitivity analysis as non responders for ORR, and events for PFS. A 90% confidence interval for PFS will also be provided.

All patients will be followed up for a minimum of 6 months. We do not expect any patient to have a follow up of less than 6 months. If a patient meets all the criteria for being evaluable but has not been followed for 6 months and has not progressed, this patient will be censored at the time of last follow up. This patient will be included in the analysis. For the determination of the decision rule for PFS (ie ≥ 10 patients event free), this patient will be considered a failure.

Date:

For safety, all patients who received at least one cycle of therapy will be included.

As per the standard of reference set by the Gynecologic Oncology Group for recurrent endometrial cancers, if a new agent has a true response rate of 10% or less, it would be considered of little clinical significance. Conversely, if the true response rate is at least 25%, further investigation is clearly indicated. These are the reference ORR numbers used to assess novel agents in the GOG-129 and 229 queue, through which nearly 20 treatments have been evaluated. As a means of comparison, and to further justify this ORR goal, the clinical data for several relevant cytotoxic and biologic agents are tabulated here.

Rx	ORR (%) [PR + CR]	PFS at 24 weeks (%)	# of Patients (n)	Reference
Etoposide	0	8.0	25	Rose et al, Gynecol Oncol 1996
Paclitaxel	25	20.8	48	Ball et al, Gynecol Oncol, 1996
Doxorubicin	9.3	23.3	43	Thigpen et al, Cancer Treat Rep. 1979,
Ixabepilone	12	20.4	49	Dizon et al, JCO, 2009
Bevacizumab	17	41.5	53	Aghajanian et al, JCO, 2011

Given the inherent difficulty in detecting meaningful overall survival (OS) data in patients who will likely frequently receive multiple, and divergent downstream agents after end of study, including possible enrollment in additional clinical trials, PFS at 24 weeks (6 months) is considered an appropriate endpoint for meaningful clinical efficacy. (Sill 2008) This approach has been adopted for recurrent and advanced endometrial cancer.

Exploratory objectives: For exploratory biomarker analyses, patients will be dichotomized on the basis of clinical benefit (CBR) rate (CR+PR+SD) as the outcome measure. Exploratory endpoints will be analyzed by treatment arm. All biomarkers without known cutoffs will be treated as continuous variables. For tissue based biomarkers, CBR will be correlated to the level of tissue expression of PD-L1 (binary: positive vs negative), or specific genes/gene signatures identified from transcriptional profiling. Non parametric 2 sample tests will be used to assess differences in the distribution of markers between the 2 groups (responders vs non responders). Archival tumor tissue IHC will be assessed only at baseline while other markers will be assessed at baseline and during treatment and their change from baseline will be analyzed. For markers such as number of infiltrating CD8+ cells and change in ICOS level expression on lymphocytes from baseline levels, we do not have established cutoffs, thus we will examine them as continuous variables. In these biomarkers we will look at changes from baseline to treatment (focused on early changes or changes within 8-12 weeks), and we explore these changes graphically in order to assess potential relationships between responders and non responders.

Date:

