
2.1 OBJECTIVES AND SCIENTIFIC AIMS

Primary Endpoints:

- Determine the effectiveness of the each arm by measuring Overall Response Rate [ORR = Complete Response (CR) + Partial Response (PR)] by RECIST v 1.1
- Determine Progression Free Survival (PFS) rate in each arm at 24 weeks (+/- 1 week)

- **Secondary Endpoints**

- Overall response rate in each arm evaluated by Immune-related Response Criteria in Solid Tumors (irRECIST) criteria. irRECIST assessments will only be completed for patients continuing treatment beyond PD
- Clinical benefit (CR + PR + Stable Disease [SD]) rate in each arm by 24 weeks +/- 7 days Duration of response in each arm
- Determine the rate of immune-related Adverse Events (irAE)
- Determine the rate of serious adverse events (SAE)
- Establish safety of each arm

Exploratory Endpoints:

- Determine the ability of the laboratory parameters to predict clinical benefit:
 - Archival tumor tissue PD-L1 expression IHC
 - Archival tumor tissue immune-related gene expression profiles
 - Archival tumor tissue IHC
 - Peripheral blood immune phenotyping
 - Peripheral blood gene expression profiling
 - Peripheral blood T cell receptor repertoire

Date:

- Peripheral blood serologic responses

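### The stated 94% power for 24-week PFS ignores the ORR gate; at the plan's own alternatives the gated power is about 84–88% and cannot exceed 90%

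*Combined protocol and SAP*

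**What the plan says.** All of the design figures are in Section 14.0, and they apply to each arm separately.

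- **ORR:** "A 10% ORR will be considered low and 25% or higher will be considered promising for further studies". The design is described so: "Forty patients provide 90% power and Type I error of 10% using a Simon two stage minimax design". An arm continues past stage 1 with at least 3 responders in 27 evaluable patients and is positive with at least 7 in 40.
- **24-week PFS:** a rate of 15% is low and 35% or more is promising. The rule is at least 10 of 40 patients progression-free. The operating characteristics are given as: "This study will have 94% power and 7% Type I error to show activity in terms of 6 months PFS rate".
- **Order of testing:** "This test of PFS rate will be performed only if the ORR analysis is significant, and thus PFS assessment is supplementary to ORR assessment". The plan uses this hierarchy to bound the overall type I error at 10%.
- **Reporting:** the PFS estimate does not depend on the test. "The Kaplan Meier estimate of median PFS will be reported as well as the PFS rate at 24 weeks", and "A 90% confidence interval for PFS will also be provided".

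The rank of the endpoint varies. Sections 1.1 and 2.1 both list it under the primary endpoints ("Determine Progression Free Survival (PFS) rate in each arm at 24 weeks (+/- 1 week"), whereas Section 14.0 names ORR as the primary endpoint and calls PFS supplementary.

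**The concern.** The plan takes the benefit of the hierarchy (control of the overall type I error) but does not carry its cost into the power. The sentence credits 94% to the study, although the study reaches the PFS test only after ORR has succeeded, and the plan gives that step 90% power. The two figures cannot both describe the same trial at the same alternatives.

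What is at stake is how the absence of a PFS claim is read. With 94% power, the lack of a claim would be fairly strong evidence against a 35% PFS rate. It is weaker evidence if the power is 84–88%, and weaker still if response is modest while disease control is good, because the PFS test is then often never run.

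**Working it through.** **Inputs, all from Section 14.0.** ORR 10% against 25%, with rule ≥3/27 then ≥7/40. 24-week PFS 15% against 35%, with rule ≥10/40. PFS is tested only if ORR succeeds. A patient without progression but with less than 6 months of follow-up counts as a failure in the PFS rule, so that rule is a plain binomial count.

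**1. Reproduce the plan's figures.** Let X be the number progression-free among 40.
- P(X ≥ 10 | 40, 0.35) = 0.9356
- P(X ≥ 10 | 40, 0.15) = 0.0672

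These round to the stated 94% and 7%. The neighbouring cut-offs do not fit: ≥9 gives 0.9697 and 0.1354, and ≥11 gives 0.8785 and 0.0299. The stated figures therefore belong to the 10-of-40 rule with no gate.

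**2. Probability of passing the ORR gate.** With x responders in the first 27 patients and Y in the next 13,

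P(gate) = Σ over x ≥ 3 of P(x | 27, p) × P(Y ≥ 7 − x | 13, p).

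| True ORR | P(gate) |
|---|---|
| 10% | 0.0977 |
| 15% | 0.3882 |
| 17% | 0.5257 |
| 20% | 0.7083 |
| 25% | 0.9001 |
| 27% | 0.9402 |
| 30% | 0.9746 |

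The rows at 10% and 25% confirm the plan's 10% type I error and 90% power for ORR. Each value is also a ceiling on PFS power at that ORR, whatever the dependence between the endpoints. The ceiling reaches 94% only at an ORR of about 27%.

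**3. Power through the gate at ORR 25% and 24-week PFS 35%.** Each patient falls into one of four cells (responder or not, progression-free or not). The joint distribution was enumerated exactly, with stage 1 truncated at ≥3/27, to give P(responders ≥ 7/40 and progression-free ≥ 10/40). The documents do not give the overlap between the endpoints, so it is varied.

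| Assumed overlap | Gated power | Gated power ÷ 0.9001 (power given ORR success) |
|---|---|---|
| No responder progression-free (extreme) | 0.8367 | 0.930 |
| Independent (0.9001 × 0.9356) | 0.8421 | 0.936 |
| 75% of responders progression-free | 0.8581 | 0.953 |
| All responders progression-free | 0.8775 | 0.975 |

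A simulation of 400,000 trials gave 0.842 for independence and 0.877 for full overlap.

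**4. Other true rates, from independence to full overlap.**
- ORR 20%, PFS 35%: 0.663 to 0.701.
- ORR 30%, PFS 35%: 0.912 to 0.931.
- ORR 17%, PFS 41.5%: 0.521 to 0.526, against 0.9904 for the PFS rule alone. These are the rates shown for bevacizumab in the plan's comparison table, where "the clinical data for several relevant cytotoxic and biologic agents are tabulated here".

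**5. Type I error.** With both nulls true (ORR 10%, PFS 15%), the gated error is 0.0066 (independent) to 0.0433 (full overlap). With ORR at 25% and PFS at 15%, it is 0.0605 to 0.0672. The 6.7% therefore remains a valid upper bound.

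**The case against.** The best defence is that the sentence follows directly after the statement of the gate and the 10-of-40 rule, so 94% can be read as the power of that rule, or of the PFS test once it is performed. Conditional on ORR success, the power at the design alternatives is 93.6% under independence and 97.5% at full overlap, so on that reading 94% is right or conservative. On this view the fault is in the labelling. That is fair as far as it goes: the number was computed correctly for the rule. But the sentence names the study rather than the rule or a conditional test, and it never says that the figure is conditional. If the conditional reading was intended, the wording still has to change.

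A second objection is that little depends on the figure. The trial is sized on ORR, and an arm that meets the ORR rule but misses the PFS rule is still called promising. PFS enters the choice between arms only in the wider review when both have exactly 7 responders. This stands, and it limits the practical effect.

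A third is that the 17%/41.5% example lies below the ORR alternative, so its 52–53% is essentially the gate's own pass probability (52.6%). This also stands. The example shows a consequence of gating on ORR; the misstatement itself is established at the plan's own alternatives.

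**Conclusion.** The concern holds. The 94% is the power of the 10-of-40 rule alone. At ORR 25% and 24-week PFS 35%, the study's probability of a formal PFS success is 84.2% to 87.8%, which is 6 to 10 points lower. The 90.0% ceiling needs no assumption about overlap. The 84–88% range assumes a relationship between response and 24-week PFS from independence to full positive overlap; even the extreme of no overlap gives 83.7%. The stated figure is nearly right only when the true ORR is well above the plan's threshold (91–93% at ORR 30%).

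This is a misreported operating characteristic. The primary ORR decision, the sample size, the 10% overall error bound and the reporting of the PFS rate with its interval are unaffected. The differing rank of 24-week PFS is a secondary inconsistency, but it bears on how much weight a reader gives the power figure.

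**What to change.** In Section 14.0, replace the power sentence with wording such as: *The PFS rule taken alone has 93.6% power and 6.7% type I error. Because PFS is tested only after ORR succeeds, the probability of showing PFS activity is about 84–88% (at most 90%) when ORR is 25% and 24-week PFS is 35%, and at most 71%, 39% and 10% when ORR is 20%, 15% and 10%.* State that the 84–88% runs from independence of response and 24-week PFS to all responders being progression-free at 24 weeks. If a shorter text is preferred, the minimum is to say that 94% and 7% refer to the 10-of-40 rule alone and to give the gated range beside them.

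Give 24-week PFS one rank, primary or supplementary, in Sections 1.1, 2.1 and 14.0.

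The cost is a few lines of text and one consistent label. Sample size, decision rules and error bound do not change; the stated power becomes less favourable.
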